3.6 VR101 Lot Traceability

VR101 devices are assigned a unique lot identifier by the contract manufacturer or J3 BIO. All components of and materials used in the finished devices are traceable to their suppliers and supplier lot numbers.

3.7 Training and procedures required to use VR101

No medical or surgical intervention or clinician involvement is required to use VR101 safely and effectively. VR101 is designed to be self-inserted by users of the device and remain in place for up to 7 consecutive days. After 7 days, the ring is removed by the user, discarded, and, at the user's discretion, replaced with a fresh ring.

VR101 is intended to be available as an OTC (Over-the-Counter) product that will not require healthcare professional assistance or supervision for use and/or as a prescription-only use device. In both cases, the user will not be assisted with use of the device. As such, the user must be able to insert and remove the device solely on the basis of reading the provided instructions for use (IFU) and labeling. Participants in CI01, the pilot clinical investigation, demonstrated, in all cases, an ability to insert and remove VR101 without physician assistance or consultation.

3.8 Sham controls

Sham control rings will be manufactured for the purpose of providing a control to enable evaluation of the efficacy of the release of the lubricating solution from VR101 in this investigation, when compared with the effects of the presence of the ring, alone. The sham control will be manufactured, packaged, and labeled identically to VR101, with the exception that the hollow ring lumen will not be filled with the glycerol solution described in Table 3. That is, the core of the sham control rings will contain no lubricating solution, but the packaging will still contain 0.25 mL of glycerol/water solution to aid in device insertion.

4 OBJECTIVES AND HYPOTHESES OF THE CLINICAL INVESTIGATION

4.1 Study Objectives

4.1.1 Primary Objectives of CI02, the Proposed Pivotal Clinical Investigation

- To demonstrate the efficacy of VR101 in treating the symptoms of vaginal dryness in women by showing that the change in VHI composite scores following 28 days of continuous VR101 use (consisting of use of 4 each VR101 devices consecutively, each for 7 consecutive days) is statistically superior to the changes in VHI composite scores following 28 days of continuous sham control use (consisting of use of 4 each sham rings consecutively, each for 7 consecutive days).
- To assess the safety of VR101 when used to treat the symptoms of vaginal dryness.

J3 Bioscience, Inc.	Clinical Investigation Plan and Protocol CI02	CI02-CIP Rev. 08 Page 23 of 75
	A Pivotal Clinical Investigation to Evaluate the Safety and Efficacy of J3 Bioscience Lubricating Intravaginal Ring VR101 in Relieving Symptoms of Vaginal Dryness	

4.1.2 Validate Claims

- Claim 1: VR101 relieves the symptoms of vaginal dryness for up to 7 days.
- Claim 2: VR101 is easy to use by following the provided instructions.
- Claim 3: VR101 is comfortable during use.

4.1.3 Demonstrate Usability

Validation of Claim 2 will justify Over-the-Counter (OTC) use of VR101.

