When the first ring is removed (Day 7, Visit 2/5 depending on study group), the participant will be asked to rate her level of agreement with the statement "the ring was easy to use by following the provided instructions" on a scale of -4 to 4 (see section 5.4.6). Claim 2 will be validated if the lower bound of the two-sided 95% confidence interval of the proportion of the study population that recorded favorable responses (participants recording a Score of 1, 2, 3 or 4) is greater than or equal to 0.80. The 95% confidence interval will be calculated using the exact test.

Claim 3: VR101 is comfortable during use.

In each daily diary, the participant will be asked to rate her level of agreement with the statement "the ring was comfortable to me today" on a scale of -4 to 4 (see section 5.4.6). Claim 3 will be validated if the lower bound of the 95% confidence interval of the proportion of the study population that recorded favorable responses (participants recording a Score of 1, 2, 3 or 4) is greater than or equal to 0.80. The 95% confidence interval will be calculated using the exact test.

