² The subject will return all rings that were expelled or were removed prior to the 5-7 days of use and could not be reinserted for any reason. See Section 5.4.3

³ May be used for any study participants (V1S2 or S1V2) who withdraw from the study between scheduled Visits

⁴ If the “EOT” visit occurs within 7 ± 2 days of final ring removal, the “Phone Call Survey” can be administered in person and an additional follow-up call is not needed

Follow-up phone calls will be conducted weekly in some weeks where the participant does not return to the clinic (days 14, 21, 63 and 70). Follow-up phone calls will also be conducted on day 35 and 147 (if applicable). The follow-up phone calls will be used to ask survey questions regarding their experience with the ring, as well as to remind participants of their responsibilities per their signed ICFs.

On days 84, 91, 98, 112, 119, 126, 133, 147, 154 and 168 no survey data will be collected, but participants will be given a reminder by phone to remove the VR101 and insert a new one.

J3 Bioscience, Inc.	Clinical Investigation Plan and Protocol CI02	CI02-CIP Rev. 08 Page 38 of 75
	A Pivotal Clinical Investigation to Evaluate the Safety and Efficacy of J3 Bioscience Lubricating Intravaginal Ring VR101 in Relieving Symptoms of Vaginal Dryness	

Visit 1/4 - First Ring Insertion

NOTE: If this is a participant's first visit, the baseline VHI assessment and IVR placement must occur on the same day. If the baseline VHI assessment and first IVR placement attempt does not occur within 30 days of initial screening procedures, determination of participant's eligibility must be re-reviewed. Participants will be asked to complete a Pre-Study survey that will gather general demographic information as well as ask questions about vaginal dryness and the effects on sexual activity.

1. Assign a unique screening identifier to each participant (different from the Participant Number) and complete initial screening procedures.
2. Participants will complete a Pre-Study Survey (Visit 1) or a Pre-Procedure Survey (Visit 4).
3. Participants will be asked to provide a urine sample for a pregnancy test.

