NOTE: If the IVR is expelled during the 7-day investigation period, the participant will be asked to rinse it using tap water and reinsert unless it is not appropriate to reinsert the expelled ring (e.g., lost in toilet, soiled). If participant is unable or unwilling to reinsert the expelled ring, she will be asked to store it, if possible, in a provided re-sealable bag and bring it to her next clinic visit. If she is unable or unwilling to reinsert the expelled ring, she will be asked to insert a new ring. Participants will be instructed to document this event in the daily diary.

Visit 2/5 - Second Ring Insertion

1. Participants will return to the clinic on day 7/56 (\pm 2 days) and submit completed daily diaries.
2. Participants will be asked to report any Adverse Events (AEs), whether or not they feel they were related to use of the investigational device. AEs will be recorded on the Adverse Event Form (Attached).
3. Participants will be asked to complete a Pre-Procedure Survey.
4. Participants will undergo a brief vaginal health assessment that will include a pH test and assessment of Vaginal Health Index (VHI) (see Table 6).
5. Participants will be instructed to remove the ring per the instructions for use and without clinician input, and will be asked to complete a post-removal survey. The survey will include a comments section for users to provide feedback on the instructions for use and any steps that were difficult to understand.
6. Participants will be asked to insert a new ring per the instructions for use and without clinician input, and to complete a post-insertion survey.
7. This ring (VR101 or sham control), followed by a third and fourth device will be used consecutively, each to remain in the vagina for 7 ± 2 days.

Visit 3/6 – Final Crossover Arm Ring Removal

1. Participants will return to the clinic on day 28/77 (\pm 2 days) and submit completed daily diaries.
2. Participants will be asked to report any Adverse Events (AEs), whether or not they feel they were related to use of the investigational device. AEs will be recorded on the Adverse Event Form (Attached).
3. Participants will be asked to complete a Pre-Procedure Survey.
4. Participants will undergo a brief vaginal health assessment that will include a pH test and assessment of Vaginal Health Index (VHI) (see Table 6).

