5.4.8 Interim Follow-Up Call Schedule

Each participant will be contacted by phone on days 14, 21, 35, 63, 70 and either day 147 (V1S2 completer), day 175 (S1V2 completer) or 7±2 days following removal of her last ring (if discontinued prior to day 147), to assess their medical condition and to complete a short questionnaire regarding their experience with ring use. If a participant is discontinued prior to completion of the safety arm and returns to the clinic for her final visit within 7±2 days following removal, all information can be collected during this visit and an additional follow-up call is not needed. For calls during ring use (days 14, 21, 63 and 70), participants will also be reminded to remove their current ring and insert the new ring on these days.

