Read ALL Instructions before inserting and removing VR101.

1. Wash and dry your hands thoroughly.
2. Remove ring from its pouch.
3. Before inserting VR101, find a position that is comfortable. You can insert the ring while lying down, squatting, or standing with one leg up, whatever position is most comfortable for you.
4. Hold the ring between your thumb and first finger, pressing opposite sides of the ring together. You may want to twist it into a figure 8.
5. It may help you to hold open the folds of skin around your vagina with your opposite hand while inserting the ring.
6. Place the tip of the ring in the vaginal opening and then push the folded ring gently into your vagina. Push the ring up and toward your back. Do not use any lubrication.
7. If you feel any discomfort, the ring probably is not inserted far enough. Try gently pushing the ring further into your vagina. The ring will not get lost in your body.
8. When you are finished, wash and dry your hands thoroughly.

Return any rings that you were unable to place for any reason to the clinic at your next visit.

Before returning a ring to the clinic, place in the original foil-lined pouch if available. If not, place in a zip lock-type bag.

Warnings:

- Do not use the ring if it appears to be damaged and/or if the package appears open or damaged.
- Do not re-insert a ring that you removed or that was expelled if it appears damaged or contaminated. You may wash it in clean water and re-insert it if it is clean. Or, use a new ring. Return any rings you chose not to re-insert to the clinic at your next visit.

VR101 Removal Instructions

Remove each VR101 ring after 7 days of use.

1. Wash and dry your hands.
2. Choose the position that is most comfortable for you.
3. Put your index finger into your vagina and hook it through the ring and gently pull downward and forward to remove the ring.
4. Discard the used ring in the trash and out of reach of children and pets. Do not flush the ring in the toilet.
5. Insert a new ring after removal of the used ring, according to the instructions provided above.

Warning: Do not re-insert a ring that you removed or that was expelled if it appears damaged or contaminated. You may wash it in clean water and re-insert it if it is clean. Or, use a new ring. Return any rings that were unable to be replaced to the clinic during your next visit. Before returning a ring to the clinic, place in the original foil-lined pouch or in a zip lock-type bag.

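### Claim 2, a self-rated ease-of-use item on one ring changed at clinic visits, can support over-the-counter use but cannot by itself justify it as Section 4.1.3 states

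*Combined protocol and SAP*

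**What the plan says.** Section 4.1.3 is a single sentence: "Validation of Claim 2 will justify Over-the-Counter (OTC) use of VR101". Section 3.7 describes what over-the-counter use demands: "the user must be able to insert and remove the device solely on the basis of reading the provided instructions for use (IFU) and labeling". The instructions in Section 5.6 include a timing step: "Remove each VR101 ring after 7 days of use".

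Under Section 4.2.3, Claim 2 is the participant's agreement, from -4 to 4, with the statement that "the ring was easy to use by following the provided instructions". It is asked when the first ring is removed. Scores of 1 to 4 are favorable, so the mildest form of agreement counts as success. The claim passes if the lower bound of the two-sided 95% exact interval for the favorable proportion is at least 0.80.

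Section 5.4.3 has the woman insert the ring herself at Visit 1/4, in a private clinic area, with printed instructions and no further information from the clinician. One who has difficulty may choose not to place it and is then withdrawn. At Visit 2/5: "Participants will be instructed to remove the ring per the instructions for use and without clinician input". Between visits there are calls. Of the crossover calls, Section 5.4.8 says "participants will also be reminded to remove their current ring and insert the new ring on these days". For the long-term phase, Section 5.4.3 says "participants will be given a reminder by phone to remove the VR101 and insert a new one", and adds that no survey data are collected on those days.

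**The concern.** The standard in 3.7 concerns ability: can a woman insert and remove the ring from the instructions and labeling alone? Claim 2 measures opinion: does she agree that doing so was easy? The two are related but different, and 4.1.3 goes from the second to the over-the-counter conclusion with nothing between.

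Two features of the design widen the gap. Women who fail at the first step leave before they can give an unfavorable rating. And the schedule supplies a visit or call on almost every day a ring is due out, so the study gives little occasion to see whether women change the ring on time without contact. If Claim 2 passes, the plan will treat over-the-counter use as justified and will not say that ring changes took place under scheduled contact.

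**Working it through.** The plan gives no sample size, power or expected rate for Claim 2, so there is no figure of its own to reproduce. Three checks follow.

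**1. Is successful unaided use measured?** Section 5.1.1 lists five endpoints: the VHI difference, dryness severity, rated ease of use, rated comfort, and the proportion of serious adverse device effects. None is a count of rings placed and removed without help. The analyses in Sections 4.2.3 and 8.1 to 8.12 add none. The conditions for observing it are nonetheless present, because women insert, remove and re-insert without clinician input at the clinic and change rings themselves between visits.

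**2. Scheduled VR101 removals against scheduled contacts.** Removal days come from Tables 4 and 5, counting from the first VR101 ring. Calls come from the text of 5.4.3 and 5.4.8.

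| Group | Removal days | At a visit | On a listed call | No listed contact |
|---|---|---|---|---|
| S1V2 | 56 to 140, every 7 days (13) | 56, 77, 105, 140 (4) | 63, 70, 84, 91, 98, 112, 119, 126, 133 (9) | none |
| V1S2 | 7, 14, 21, 28, then 84 to 168, every 7 days (4 + 13 = 17) | 7, 28, 105, 140, 168 (5) | 14, 21, 84, 91, 98, 112, 119, 126, 133, 147, 154 (11) | 161 |

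By the text, S1V2 has 4 + 9 = 13 of 13 and V1S2 has 5 + 11 = 16 of 17, together 29 of 30. The Table 4 reminder row, as extracted, has no mark for days 147, 154 and 161. That gives 17 - 3 = 14 of 17 for V1S2, and 27 of 30 overall. The Table 4 heading does label that column as a phone call, and the text lists day 168 but not 161, so these entries need to be reconciled.

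**3. Can withdrawn placement failures change the result?** The exact lower bound for x favorable out of n is the 0.025 quantile of Beta(x, n - x + 1). Group sizes at first VR101 use are not given. Section 5.3.6 reports 72 enrolled, so I take 36 (one group, assuming an equal split) and 72 (both groups). Both are shown because 4.2.3 refers to both groups and 8.12 to V1S2 only. Two placement failures are assumed for illustration.

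| Starting n | Failures left out | Lower bound | Failures counted | Lower bound |
|---|---|---|---|---|
| 36 | 32 of 34 | 0.803 (passes) | 32 of 36 | 0.739 (fails) |
| 72 | 63 of 70 | 0.805 (passes) | 63 of 72 | 0.776 (fails) |

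With no failures left out, the pass marks are 34 of 36 (bound 0.813) and 65 of 72 (bound 0.810). The plan gives no expected failure rate. The table shows only that two such women could decide a borderline result.

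**The case against.** The strongest reply is that the design does put use from the instructions to work. Clinicians add nothing to the printed sheet, removal and re-insertion are done without their input, and the Appendix B item asks about the whole experience from insertion to removal. A visit or call tells a woman when to change the ring, not how. All of this stands. A reader might infer that use from the instructions alone is untested; the documents contradict that.

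Three other stronger readings also go too far:

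- *That 3.7 demands unprompted timing.* It speaks of inserting and removing. The 7-day step is in the instructions, but joining the two is a reading, not something the plan states.
- *That timely removal is recorded nowhere.* The case report forms and diary templates are not in the text available. Section 5.3.5 has diaries record the date and time of mid-week removals and new insertions. What can be said is that no stated endpoint or analysis uses such data.
- *That every removal on a contact day was prompted, or that at most 3 of 17 could be unprompted.* Rings stay in for 7 ± 2 days, so a woman may change before the call, and restarts move changes off the nominal days. The counts are of scheduled contacts only.

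It is also fair to say that Claim 2 is tested only after efficacy, safety and Claim 1 succeed, that 3.7 reports pilot participants inserting and removing the ring without physician assistance in all cases, that prescription-only use remains open, and that Section 8.5 keeps the claims out of study success. These limit the consequence. They do not repair 4.1.3, which cites none of them and rests the conclusion on Claim 2. The pilot statement is the kind of performance figure this study could report and does not plan to.

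**Conclusion.** The point holds in a limited form. Insertion and removal technique is exercised from the printed instructions, and a favorable Claim 2 result would be relevant evidence. It does not by itself justify over-the-counter use, for three reasons: it is a rating rather than a measure of success; women who cannot place the ring are outside its denominator; and changing the ring on time without scheduled contact is assessed by no stated endpoint, since 29 of 30 scheduled VR101 removals by the text (27 of 30 by the table row) coincide with a visit or call.

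The counts assume nominal days and the tables as extracted. The denominator illustration assumes 36 or 72 women and two failures. The unseen forms may hold useful data, but no planned analysis draws on them. Trial success is unaffected; what changes is the conclusion that may be drawn from Claim 2.

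**What to change.** 1. Reword 4.1.3 to say that Claim 2 supports, but does not by itself justify, over-the-counter use, and state that ring changes in the study were made under scheduled visits and reminder calls.
2. Beside the Claim 2 rating, report the proportion of first VR101 rings inserted and removed by the participant without help, with its exact 95% interval. Count women who attempted but could not place the ring as failures. Take the data from the Post-Insertion and Post-Removal surveys, adding a yes/no item if they lack one. Section 8.4 already reports crossover withdrawals, so for women past their first VR101 ring the table must come from completed forms and withdrawal records; a new item would serve only later or replacement participants.
3. Optionally, on the remaining long-term calls, ask before the reminder whether the ring has already been changed. After weeks of reminders this is only partly informative and should be descriptive.

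No change to wear time or to the reminders is proposed. The cost is a protocol wording change, one extra table, possibly one survey item, and a narrower over-the-counter statement.

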4.1.4 Conduct Exploratory Evaluations

Additional survey questions may be asked of participants to further the scientific and technical understanding of VR101, as well as user preferences.

4.2 Hypotheses of the Clinical Investigation

The clinical investigation CI02 is designed to demonstrate that the efficacy and safety of VR101 are substantially equivalent to the safety and efficacy of the predicate device, Replens® Long-lasting Vaginal Moisturizer in Pre-Filled Applicators. Substantial Equivalence will be assessed through the evaluation of the ability of clinical use of VR101 to meet safety and efficacy endpoints.

4.2.1 Primary Efficacy Hypothesis

Primary Efficacy Hypothesis: VR101 will relieve symptoms of vaginal dryness to a degree statistically superior to that of a sham control, when assessed objectively by a clinician who assigns VHI scores before and following 28 consecutive days of VR101 and sham control use (4 VR101 devices or shams used consecutively, each for 7 consecutive days).

The relief of vaginal dryness symptoms will be assessed throughout the study using composite Vaginal Health Index (VHI) scores, which are a sum of clinician-assigned scores for Vaginal Elasticity, Fluid Volume, Epithelial Integrity, Moisture and pH each weighted equally. This identical VHI composite score was used to evaluate the effectiveness of the predicate device (Replens) in clinical investigations that supported 510(k) premarket notification K101098, cleared by the FDA to allow marketing of the Replens device in the US.

Δ VHI resulting from use of VR101 or the sham control will first be determined by subtracting a participant's baseline VHI score from her day 28 VHI score, when using either the VR101 or the sham control. For example, if a participant's baseline VHI composite score is 15 and her VHI score following use of VR101 for 28 days is 22, Δ VHI_{VR101} at day 28 would be 22 – 15 = 7.

Superiority of VR101 to the sham control will be demonstrated if the *p*-value associated with a two-tailed Student's t-test evaluating the mean of the paired differences Δ VHI_{VR101} (day 28)

J3 Bioscience, Inc.	Clinical Investigation Plan and Protocol CI02	CI02-CIP Rev. 08 Page 24 of 75
	A Pivotal Clinical Investigation to Evaluate the Safety and Efficacy of J3 Bioscience Lubricating Intravaginal Ring VR101 in Relieving Symptoms of Vaginal Dryness	

and ΔVHI_{sham} (day 28) is less than 0.05. If the paired differences observed are not normally distributed, an appropriate non-parametric test will be substituted for the two-tailed Student's t-test. Additionally, a two-tailed 95% confidence interval of the mean paired difference will be reported.

The same 95% confidence interval for the menopausal population (see section 8.12) will be reported.

NOTE: It is possible to demonstrate statistical superiority and for the mean value of ΔVHI_{VR101} (day 28) to be less than or equal to zero. Efficacy of VR101 will only be demonstrated if VR101 statistical superiority is demonstrated AND the mean value of ΔVHI_{VR101} (day 28) is greater than 0. That is, use of VR101 must not only be superior to that of the sham control, but must also demonstrate a positive improvement in VHI score.

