8 STATISTICAL CONSIDERATIONS

8.1 Summary of Statistical Methods

The hypotheses of the clinical investigation are detailed in Section 4.2. For Primary Efficacy and Validation of Claim 1, the null hypothesis will be rejected based on a two-tailed Student's t-test ($\alpha = 0.05$) or an appropriate non-parametric two-tailed test if the data do not appear to be normally distributed.

The remainder of hypotheses will be tested using the 95% confidence interval associated with a proportion of events (e.g. SADE occurrence per number of devices used, proportion of favorable survey responses).

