8.2 Sample Size Determination based on Statistical Power to Show Efficacy

A mean power analysis was performed to determine the number of participants required to demonstrate superiority in Δ VHI scores (baseline VHI minus adjusted VHI) between VR101 and a sham ring (improvement of vaginal dryness symptoms).

In the pilot clinical investigation of VR101, the mean and standard deviation of paired differences in VHI composite scores was 1.19 ± 2.35 . This composite score included an estimate of scaled pH (see Section 5.4.4) which was a value estimated based on values obtained on day 14 (following consecutive use of two VR101 devices, each for 7 consecutive days), and day 0 (baseline). These data represent the data collected in the pilot study that are most similar to the proposed Primary Efficacy Endpoint, but conservatively assume the sham ring does not affect

J3 Bioscience, Inc.	Clinical Investigation Plan and Protocol CI02	CI02-CIP Rev. 08 Page 53 of 75
	A Pivotal Clinical Investigation to Evaluate the Safety and Efficacy of J3 Bioscience Lubricating Intravaginal Ring VR101 in Relieving Symptoms of Vaginal Dryness	

VHI scores.

The maximum VHI score is 25 (there are 5 components of the VHI, each of which can be assigned a score of a maximum of "5"). Participants with an initial baseline VHI of 23 or higher will be excluded from study enrollment, as these participants' scores indicate that they do not, from an objective assessment (VHI) standpoint, present with symptoms indicative of vaginal dryness- a majority (at least 3 of 5) of VHI component scores are "perfect" "5"s. With the exclusion from the CI01 data set of participants' VHI scores who were 23 or higher at the initiation of the study, the mean and standard deviation of 14-day Δ VHI scores recorded in CI01 was 1.78 ± 2.14 . A sample size of 60 participants receiving both sham rings and active devices in the proposed crossover investigation will have 99% power to detect a difference in Δ VHI means of 1.78 assuming a standard deviation of differences of 2.14, using a paired t-test with a 0.05 two-sided significance level.

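### The primary superiority rule in 4.2.1 should state its direction and rest on one test named before unblinding

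*Combined protocol and SAP*

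**What the plan says.** The direction is clear in the aims. The objective in 4.1.1 is that the VR101 change "is statistically superior to the changes in VHI composite scores following 28 days of continuous sham control use", and the hypothesis in 4.2.1 is that "VR101 will relieve symptoms of vaginal dryness to a degree statistically superior to that of a sham control".

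The decision sentence in 4.2.1 is "Superiority of VR101 to the sham control will be demonstrated if the *p*-value associated with a two-tailed" Student's t-test on the mean of the paired differences "day 28) is less than 0.05". It attaches no sign to that mean. Section 8.1 repeats the two-tailed rule. Section 8.5 ties trial success to rejecting the null hypotheses as defined in 4.2.1 and 4.2.2.

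A NOTE in 4.2.1 adds a second condition: "Efficacy of VR101 will only be demonstrated if VR101 statistical superiority is demonstrated AND the mean value of" the VR101 change at Day 28 is above 0.

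On the choice of test, 4.2.1 substitutes a suitable non-parametric test if the observed differences are not normal, and 8.1 allows the t-test "or an appropriate non-parametric two-tailed test if the data do not appear to be normally distributed". Neither section names the substitute, sets a criterion for normality, or says who decides and when. The 95% confidence interval to be reported is that of the mean in either case.

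On sign, 4.2.1 defines the change as Day 28 minus baseline with a worked example (22 − 15 = 7), and 5.1.1 orders the difference as VR101 minus sham. The parenthesis in 8.2 reverses the subtraction ("baseline VHI minus adjusted VHI) between VR101 and a sham ring").

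**The concern.** This is the pass/fail rule of a pivotal trial, so its wording should decide the outcome without interpretation. A two-tailed p-value below 0.05 arises equally when sham is better. The second condition compares VR101 with its own baseline, not with sham, so it closes the gap only when the VR101 mean change is not positive. Other rules in the same document do carry a direction: safety uses an upper confidence limit (4.2.2), and Claims 2 and 3 use lower limits (4.2.3).

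The open choice of test is a separate matter. Section 9 has the sponsor enter the data after the study is opened and makes them available for analysis once the blind can be broken. Nothing requires the test to be fixed before then. If the t-test and its substitute fall on different sides of 0.05, the plan does not say which one counts. A rank-based p-value could also disagree with the reported interval for the mean.

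**Working it through.** **1. The plan's own power (8.2).** Inputs: n = 60, SD of differences 2.14, true difference 0.89, "using a paired t-test with a 0.05 two-sided significance level".
- Standard error = 2.14/√60 = 0.276.
- Non-centrality = 0.89/0.276 = 3.22; critical t on 59 df = 2.001.
- Power from the noncentral t = 88.7%, against 88% stated. For a difference of 1.78 it is above 99.9%, against 99% stated.

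The stated figures hold.

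**2. What the p-value rule accepts.** Significance needs an observed mean difference beyond ±2.001 × 0.276 = ±0.55, on either side. By symmetry, if VR101 is truly 0.89 worse than sham, p < 0.05 occurs 88.7% of the time.

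**3. Adding the positive-mean condition.** The documents give no SD for the sham change. I assume SD 2.14 for each change, which with SD 2.14 for the differences implies a correlation of 0.5. Results are from 40,000 simulated trials per row, n = 60.

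| True mean change, VR101 / sham | Literal rule met | Met with sham significantly better | Met if VR101 must also exceed sham |
|---|---|---|---|
| 1.78 / 0.89 | 88.6% | 0% | 88.6% |
| 0.89 / 1.78 | 88.6% | 88.6% | 0% |
| 0.30 / 1.19 | 75% | 75% | 0% |
| −0.89 / 0 | below 0.01% | below 0.01% | 0% |
| −1.78 / −0.89 | 0% | 0% | 0% |
| 0.89 / 0.89 | 5.0% | 2.5% | 2.5% |
| 0 / 0 | 2.4% | 0.2% | 2.2% |

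The gap matters only when the VR101 mean change is positive and the sham change is larger. Adding the direction leaves the planned power at 88.6%.

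**4. Choice of test, well-behaved data.** Null differences were drawn as normal with SD 2.14 and rounded to whole points (20,000 data sets, n = 60). Type I error was:
- t-test: 5.0%
- Wilcoxon signed-rank: 4.9%
- t or Wilcoxon according to a Shapiro-Wilk check: 5.0% (5.2% in a second run at n = 61)
- smaller of the two p-values: 5.6% (5.8% in the second run)

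Power at 0.89 in the second run was 88.8% for t and 88.4% for t-then-Wilcoxon.

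**5. Choice of test under the 8.8 imputation.** Section 8.8 gives a participant who misses a whole treatment period the lowest VR101 change or the highest sham change. Section 8.4 reports 11 of 72 withdrawn during the crossover, but not how many missed a whole period, so the splits below are assumptions. Settings: n = 72, SD 2.14, correlation 0.5, changes rounded to whole points, 6,000 trials each.
- Two missing VR101 and two missing sham, true changes 1.78 and 0.89: power is 54% (t) and 64% (Wilcoxon). The tests disagree in 11% of trials, nearly always with Wilcoxon significant and t not.
- Five missing one period and six the other, true changes 1.78 and 0: power is 86% (t) and 92% (Wilcoxon). They disagree in 7% of trials.

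Other runs on these two splits gave disagreement in up to about 10 to 12% of trials and power gaps of about 7 to 11 points. The overall loss of power here comes from the imputation rule, which is a separate matter.

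**The case against.** The strongest reply is that the direction is not in doubt. The objective, the hypothesis and the endpoint rationale in 6.4 all say VR101 is to be superior to sham. The NOTE in 4.2.1 repeats that VR101 must beat sham as well as improve on baseline. A two-tailed 0.05 test paired with a directional hypothesis is ordinary practice, and the confidence interval would show the direction. This stands: a result with sham significantly better would contradict the plan's own text. A reader might infer that the plan would accept an inferior ring, but the documents do not support that when read together. The 89% is also a selected case, as the table shows.

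A reader might also infer that the reversed subtraction in 8.2 helps to create the gap. It does not. A two-sided p-value is unchanged when the sign is flipped, the worked example in 4.2.1 fixes the sign, and 8.2 itself treats +1.78 as an improvement.

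On test choice, the pilot study used the Wilcoxon signed-rank test (2.4), so that is the natural substitute, and with clean data the cost is close to nil. That stands too. Larger error rates can be produced by admitting a sign test, but the documents never mention one. The reply does not cover the imputed data, where the choice can decide the result.

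**Conclusion.** The point holds as two gaps in the wording of a pivotal decision rule. It is not an error in the design or in the stated power.

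First, the operative sentence lacks the direction that the rest of the plan supplies. Taken literally it would be met about 89% of the time with sham truly 0.89 better (means 0.89 and 1.78), but almost never when the VR101 mean change is clearly negative. This rests on n = 60, SD 2.14 and an assumed correlation of 0.5.

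Second, and more consequential in practice, the primary test depends on the observed data, with no named alternative, no criterion and no requirement to choose before unblinding. The cost is small with well-behaved data. Under worst-case imputation the candidate tests can give opposite answers in up to about 10 to 12% of trials, depending on the assumed number and split of participants missing a whole period and on the true effect.

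The 8.2 parenthesis is a clerical slip and contributes to neither gap.

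**What to change.** In 4.2.1 and 8.1, state that superiority is shown if the lower limit of the two-sided 95% confidence interval for the mean of (change on VR101 minus change on sham) is above 0. Specify that this comes from one primary analysis named before the blind is broken and used whatever the distribution. Keep the condition that the mean VR101 change exceeds 0. Report the Wilcoxon signed-rank result as a sensitivity analysis only. In 8.2, change the parenthesis to Day 28 minus baseline.

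The cost is protocol and SAP wording, with the sponsor and IRB approval that Section 10 requires, before unblinding. The sample size stays at 60 completers and the planned power at about 88%. There is one small downside: under heavy worst-case imputation the mean-based analysis can have somewhat lower power than the rank test, as step 5 of the working shows. The sponsor should accept that knowingly when naming the primary analysis.
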